10.3.4 Definitions for Assessment Windows

For the purpose of data analysis, *baseline* measures will be the last measurements taken before the subject receives the study medication. Because this study requires a single dose of formulation, all measures taken after the subject has received the study medication will be considered *on-treatment* and *end-of-treatment measures*. The height and weight collected on the day of dosing will be used for all calculations.

10.4 Study Population Summaries

Population summaries will be provided for the pharmacokinetic population included in this study.

10.4.1 Disposition

The summary tables will provide frequency counts for subject disposition (all treated subjects, subjects who completed the study, subjects who discontinued from the study and reason for discontinuation). Identification numbers for discontinued subjects will also be included in the tables.

Disposition in terms of number of subjects excluded from each analysis population (safety and pharmacokinetic) will also be provided.

10.4.2 Demographics

The demographic summary will include descriptive statistics for age, sex, race, weight, and height.

10.4.3 Protocol Violations

All protocol violations and deviations will be tabulated.

10.4.4 Treatment Compliance

No formal summary of treatment compliance will be produced.

10.4.5 Prior and Concomitant Medications

All concomitant medications will be tabulated.

10.4.6 Efficacy Analysis

No efficacy assessment is planned for this study.

10.5 Safety and Tolerability Evaluations

Analyses will be provided.

Confidential

10.5.1 Extent of Exposure

No formal extent-of-exposure analysis will be produced.

10.5.2 Adverse Events

MedDRA will be used to classify all AEs with respect to system organ class and preferred term. The dictionary version will be recorded in the clinical study report.

10.5.3 Clinical Laboratory Tests

Screening laboratory values will be preserved in source documentation.

10.5.4 Vital Sign Measurements

Vital sign values will be contained in the data listings.

10.5.5 Electrocardiograms

No formal analysis of abnormal ECG findings will be produced.

10.5.6 Subgroup Analyses

All analyses will be provided for the overall group.

10.5.7 Summaries of Pharmacokinetic Endpoints

All pharmacokinetic parameters for the concentrations of d- and l-amphetamine in plasma (including C_{max} , t_{max} , AUC_{0-t} , $AUC_{0-\infty}$, and $t_{\frac{1}{2}}$) will be estimated for each treated subject.

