	 with the written approval of the Sponsor or Medical Monitor 9. Abnormal clinically significant laboratory test values at screening that, in the opinion of the Sponsor or Medical Monitor would preclude study participation 10. Known history of allergy/hypersensitivity to amphetamine or any of the components of DYANAVEL XR, heparin flush and topical anesthetics 11. Parent or guardian's inability or unwillingness to follow directions of the Investigator or study research staff 12. Any uncontrolled medical condition that in the opinion of the Sponsor or Medical Monitor would preclude study participation 13. History of significant illness requiring hospitalization, or surgery requiring anesthetics within 30 days of dosing.
Assessments:	 K-SADS-PL Adverse Events Electrocardiogram Safety Labs Physical Exam Vital Signs Medical History Concomitant Medications
Criteria for evaluation:	Pharmacokinetics : The pharmacokinetic parameters for the concentrations of d- and l-amphetamine in plasma will be determined for each subject receiving study medication.
Statistical methods:	 Sample size determination: The sample size for this study was powered per FDA instruction. 4 - 6 subjects aged 4 to 5 years will provide adequate power for a pharmacokinetic analysis. Study populations: Adverse events will be reported for all subjects once enrolled. Total and treatment-emergent adverse events will be reported. All subjects with sufficient plasma concentration data for estimating pharmacokinetic parameters will be included in the pharmacokinetic analyses. Pharmacokinetic analysis: Pharmacokinetic parameters will be summarized and no formal comparisons will be made. Pharmacokinetic plasma samples: All PK Plasma samples will be sent frozen to the analytical lab after the end of the study. Safety analysis: MedDRA, current version will be used to classify all AEs with respect to system organ class and preferred term.
Safety:	Adverse Event (AE) collection

TABLE OF CONTENTS

SPONSOR'S	SIGNATURE	2
INVESTIGAT	OR'S SIGNATURE	3
PROCEDURE	S IN CASE OF EMERGENCY	4
TABLE OF CO	ONTENTS	8
LIST OF ABB	REVIATIONS	. 11
1.0	INTRODUCTION	. 13
2.0	STUDY OBJECTIVE	. 15
3.0	INVESTIGATIONAL PLAN	. 16
3.1	Overall Study Design	. 16
3.2	Rationale for Study Design and Control Groups	. 16
4.0	SELECTION AND WITHDRAWAL OF SUBJECTS	. 18
4.1	Inclusion Criteria	. 18
4.2	Exclusion Criteria	. 18
4.3	Discontinuation of Subjects	. 19

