10.5.7	Summaries of Pharmacokinetic Endpoints	35
10.5.8	Interim Analyses	35
11.0	DIRECT ACCESS TO PROCEDURAL DOCUMENTS	36
12.0	QUALITY CONTROL AND QUALITY ASSURANCE	38
13.0	ETHICS	39
14.0	DATA HANDLING AND RECORD KEEPING	12
15.0	REFERENCES	13
16.0	APPENDICES	14
APPENDIX B	PK SAMPLES PROCESSING AND HANDLING	45

LIST OF ABBREVIATIONS

Abbreviation	Definition
ADHD	Attention-deficit hyperactivity disorder
AE	Adverse event
AUC	Area under the concentration-time curve
$AUC_{0-\infty}$	Area under the concentration-time curve from Time 0 to infinity
AUC _{0-t}	Area under the concentration-time curve from Time 0 to last sampling time (t) with a quantifiable plasma drug concentration
AUC ₀₋₁₂	Area under the concentration-time curve from Time 0 to 12 hours after dosing
CFR	(United States) Code of Federal Regulations
°C	degrees Centigrade
C _{max}	Peak (maximum) observed plasma drug concentration
CRF	case report form
D	Day
DSM-5	Diagnostic and Statistical Manual of Mental Disorders, 5 th edition
ECG	Electrocardiogram
ER	extended release
°F	degrees Fahrenheit
FDA	(United States) Food and Drug Administration
GCP	Good Clinical Practice
Н	Hour
HCl	Hydrochloride
HR	Heart Rate
ICH	International Conference for Harmonization
IEC	Independent Ethics Committee
IRB	Institutional Review Board
K-SADS-PL	Kiddie-SADS Present and Lifetime Version
kg	Kilogram
L	Liter
m^2	square meters
MedDRA	Medical Dictionary for Regulatory Activities
mg	Milligram
min	Minute
mL	Milliliter
РК	Pharmacokinetic

Abbreviation	Definition
SAE	serious adverse event
t _{1/2}	terminal-phase elimination half-life
t _{max}	time to peak (maximum) observed plasma drug concentration
US	United States
USP	United States Pharmacopeia
WBC	white blood cell

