10.2 Study Endpoints

10.2.1 Pharmacokinetic Endpoints

The pharmacokinetic parameters for the concentrations of d- and l-amphetamine in plasma will include C_{max} , t_{max} , AUC_{0-t} , $AUC_{0-\infty}$, and $t_{\frac{1}{2}}$. Mean, geometric mean, standard deviation, and percentage coefficient of variation will be calculated for the pharmacokinetic data, within the context of limited samples which can be collected from a pediatric population.

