10.3 General Considerations for Statistical Analysis

10.3.1 Analysis Populations

All treated subjects will be included in the analysis for safety and tolerability assessments. All subjects with sufficient plasma concentration data for estimating pharmacokinetic parameters will be included in the pharmacokinetic analyses.

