10.3.3 Procedures for Handling Missing Data

In general, no imputation will be done for missing data. However, AEs with missing severity assessments will be assigned as "severe," and AEs with missing relationship assessments will be assigned as "related" for the purpose of analysis.

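### Does leaving sufficient PK data undefined let a child without a 28 h sample distort the mean AUC0-t?

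*Combined protocol and SAP*

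**What the plan says.** Section 10.5.7 names Cmax, tmax, AUC0-t, AUC0-∞ and t½ and says that they "will be estimated for each treated subject". The synopsis (Criteria for evaluation) agrees: parameters "will be determined for each subject receiving study medication". The rule on who is analysed is in section 10.3.1: "All subjects with sufficient plasma concentration data for estimating pharmacokinetic parameters will be included in the pharmacokinetic analyses". No section gives a minimum number of samples, a required time point or a rule per parameter.

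The List of Abbreviations defines AUC0-t as running "from Time 0 to last sampling time (t) with a quantifiable plasma drug concentration". Section 5.1.3.1 sets draws before dosing and at 1, 3, 4, 6, 8, 10, 12 and 28 h, the last with a 26-30 h window. Section 10.3.3 adds: "In general, no imputation will be done for missing data". Section 10.2.1 gives the summaries: "Mean, geometric mean, standard deviation, and percentage coefficient of variation will be calculated for the pharmacokinetic data". On exclusions, section 10.4.1 says: "Disposition in terms of number of subjects excluded from each analysis population (safety and pharmacokinetic) will also be provided".

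**The concern.** Two statements seem to pull apart: every treated child gets every parameter, yet only children with sufficient data are analysed, and sufficiency is left open. The sampling scheme gives that consequence. The 28 h draw is the only post-dose sample that falls outside required confinement, since a child may go home at about 13 h and be brought back (sections 5.1.2 and 5.1.7). If the child does not return, AUC0-t by its own definition becomes an area to 12 h or earlier. Nothing in the text expressly forbids averaging it with areas to 28 h.

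The study has 4-6 children, and one who withdraws after dosing is not replaced (section 4.3.1), so one case is enough to move the summary. Mean exposure would look lower and more variable because of a sampling gap, in data that section 2.0 says will guide dosing in later studies. An inclusion rule chosen after the concentrations are known could also be criticised as data-dependent.

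**Working it through.** **The plan's own figure.** The documents give no number for truncation. Section 10.1 gives 4-6 subjects and adult between-subject variability of about 20%, with no precision target, so the sample size cannot be re-derived. What it implies is a 95% CI for a geometric mean of exp(± t(0.975, n−1) × 0.198/√n), where 0.198 = √ln(1 + 0.20²). This is 73-137% of the estimate at n = 4 and 81-123% at n = 6.

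**Inputs for the truncation check** (section 1.0, ages 6-12, fasting, 10 mg): tmax 3.9 h (d) and 4.5 h (l); half-life 10.43 h, SD 2.01 (d) and 12.14 h, SD 3.15 (l). The one-compartment shape is an assumption, as is carrying these values over to ages 4-5.

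**Profile.** ke = ln 2/half-life = 0.0665 (d), 0.0571 (l). Solving ln(ka/ke)/(ka − ke) = tmax gives ka = 0.652 (d), 0.567 (l). Per unit of dose over volume,

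AUC0-x = ka/(ka − ke) × [(1 − e^(−ke·x))/ke − (1 − e^(−ka·x))/ka], and AUC0-∞ = 1/ke.

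| | AUC0-12 | AUC0-28 | AUC0-∞ | r = AUC0-12/AUC0-28 | Extrapolated beyond 28 h | Extrapolated beyond 12 h |
|---|---|---|---|---|---|---|
| d | 7.50 | 12.44 | 15.05 | 0.603 | 17.3% | 50.2% |
| l | 7.70 | 13.58 | 17.51 | 0.567 | 22.5% | 56.0% |

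**One truncated child among n, otherwise equal areas.** The geometric mean falls by 1 − r^(1/n) and the arithmetic mean by (1 − r)/n.

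| | Geometric, n = 4 | Geometric, n = 6 | Arithmetic, n = 4 | Arithmetic, n = 6 |
|---|---|---|---|---|
| d | 11.9% | 8.1% | 9.9% | 6.6% |
| l | 13.2% | 9.0% | 10.8% | 7.2% |

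**Sensitivity.** The geometric-mean shift ranges from 6.3% (d half-life assumed to be 7 h, n = 6) to 15.0% (l at 15.29 h, linear trapezoid on the protocol times, n = 4).

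**Reported CV.** √{[(n − 1) × 0.04 + 0.04r² + (1 − r)²]/n} ÷ [(n − 1 + r)/n] gives 30.0% (d) and 31.7% (l) at n = 4, and 26.7% and 27.8% at n = 6, against 20% without truncation.

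**Chance of a missed draw.** The documents give no rate. At an assumed 2%, 5% or 10% per child, 1 − (1 − p)^n is 8%, 19% or 34% (n = 4) and 11%, 26% or 47% (n = 6).

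**The passages side by side.** Section 10.5.7 says what is estimated for each child and does not say that every estimate is pooled. Section 10.3.1 says who enters the analyses and ties sufficiency to being able to estimate the parameters. Read together: derive what can be derived for each child, and summarise those whose data support it. Section 10.4.1 presupposes that some children may be excluded.

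**Would a truncated value be noticed?** Actual sampling times are recorded (sections 3.2 and 5.1.3.1), deviations are tabulated (section 10.4.3), and the shipment memo lists missing samples (Appendix B). Parameters are obtained child by child. Among 4-6 children, an area ending at 12 h is plain to see.

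**The case for a change.** The strongest case for writing a rule is that the event is foreseeable and the text would be cheap. It needs no extra blood, and the List of Abbreviations already contains an area to 12 h ("Area under the concentration-time curve from Time 0 to 12 hours after dosing") that is not an endpoint and could serve as a common-interval summary. Cmax and tmax do not depend on the 28 h sample while AUC0-t, AUC0-∞ and t½ do, so one undivided notion of sufficiency is coarse. A 28 h sample drawn but below the assay limit truncates AUC0-t in the same way. All of that is correct, and so is the arithmetic above.

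It does not establish a need to amend. The plan also works against the missed draw: children may stay overnight, the last draw has a four-hour window, usual ADHD medication resumes only after that sample (section 3.1), and those who stop early are encouraged to complete the final visit (section 4.3.1).

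Fuller rules bring costs of their own:

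- Substituting a value such as half the assay limit at 28 h would depart from the AUC0-t definition and from the general no-imputation rule in section 10.3.3.
- An extrapolation ceiling of, say, 35% would remove fully sampled children. Simulation used the section 1.0 half-life means and SDs (floored at 4 h) with 5% or 10% residual error. For l-amphetamine, 6.4% or 8.5% of complete profiles failed. At least one child would then be lost in 1 − 0.936⁴ = 23% to 1 − 0.915⁴ = 30% of studies at n = 4, and in 33-41% at n = 6. Those removed are selectively the long half-lives. This is more frequent than a missed draw at an assumed 5% per child (19% and 26%).
- Excluding a child also costs precision: at 20% CV the interval widens from 73-137% (n = 4) to 61-164% (n = 3), or from 81-123% (n = 6) to 78-128% (n = 5).
- A 12 h area covers only about 50% (d) or 44% (l) of AUC0-∞, so it would supplement the stated measures and not replace them.

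What stands is that the threshold is unwritten and that a literal reader could pool a truncated area.

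**Conclusion.** No change to the plan is needed. If a 28 h draw is missed and the child is still averaged, the geometric mean AUC0-t falls by about 8-13% (6-15% across sensitivities) and the arithmetic mean by about 7-11%. Both conditions must hold. The first has no documented rate, and the second runs against the sensible reading of section 10.3.1. The size rests on a one-compartment profile, values from older children after a fasting 10 mg dose, equal true exposure across children and a single missed draw.

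The study is descriptive, with no formal tests (section 10.3.2), and each child's values and sampling times are available. An analyst would ordinarily keep such a child's Cmax and tmax, leave the truncated area out of the AUC0-t summary or flag it, and show the number contributing to each statistic. Section 10.3.1 permits this and section 10.4.1 makes exclusion from the PK population visible. An amendment with IRB approval (section 13.7) to record that practice would gain little.

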10.5.8 Interim Analyses

No interim analysis is planned for this study.

11.0 DIRECT ACCESS TO PROCEDURAL DOCUMENTS

11.1 Study Monitoring

According to ICH GCP guidelines, the Sponsor of the study is responsible for ensuring the proper conduct of the study with regard to protocol adherence and validity of data recorded on the eCRF. Tris Pharma and its designated CRO are responsible for assigning the study monitor(s) to this study. The study monitors' duties are to aid the Investigator and its designated CRO in the maintenance of complete, accurate, legible, well-organized, and easily retrievable data. The study monitor will advise the Investigator of the regulatory necessity for trial-related monitoring, audits, IRB review, and inspection by providing direct access to the source data/documents. In addition, the study monitor will explain to and interpret for the Investigator all regulations applicable to the clinical evaluation of an investigational drug as documented in ICH guidelines.

It is the study monitors' responsibility to inspect the eCRFs throughout the study to protect the rights of the subjects; to verify adherence to the protocol; to verify completeness, accuracy, and consistency of the data; and to confirm adherence of study conduct to any local regulations. Details will be outlined in the study monitoring plan.

11.2 Source Documents

Tris Pharma requires that the Investigator prepare and maintain adequate and accurate records for each subject treated with the investigational drug. Source documents such as any hospital, clinic, or office charts and the signed informed consent forms are to be included in the Investigator's files with the subject's study records.

Data will be captured electronically. Study site personnel will record eCRF data from source documents. If any data are first recorded onto documents such as laboratory reports, these documents will be considered source.

11.3 Data Collection Management

This study will use electronic data collection techniques to collect data directly from the investigational site using eCRFs. The data will be stored centrally in a fully validated clinical database compliant with FDA regulations on electronic data integrity. The Investigator is responsible for ensuring that all sections of each eCRF are completed promptly and correctly and that entries can be verified against any source data.

Study monitors will perform 100% source document verification to ensure there are no inconsistencies between the eCRFs and source documents. Discrepancies will be resolved in accordance with the principles of GCP. Detailed study monitoring procedures are provided in the Clinical Monitoring Plan.

At intervals throughout the study and upon completion, data will be exported from the database into SAS datasets.

Data management will be coordinated by the data managers of Tris or its designate in accordance with their SOPs for data management and a formal study data management plan. The data managers will provide a quality control statement following database lock.

Adverse events will be coded with the Medical Dictionary for Regulatory Activities (MedDRA). Concomitant medications will be coded using World Health Organization – Drug Reference List.

12.0 QUALITY CONTROL AND QUALITY ASSURANCE

Quality assurance includes all the planned and systematic actions that are established to ensure that the clinical study is performed and the data are generated, documented (recorded), and reported according to ICH GCP and local/regional regulatory standards.

A quality assurance representative from Tris Pharma (or a qualified delegate), who is independent of and separated from routine monitoring, may periodically arrange inspections/audits of the clinical study by reviewing the data obtained and procedural aspects. These inspections may include on-site inspections/audits and source data checks. Direct access to source documents is required for the purpose of these periodic inspections/audits.

13.0 ETHICS

13.1 Ethics Review

This study will be conducted according to GCP; US 21 Code of Federal Regulations (CFR) Part 50 (Protection of Human Subjects); US 21 CFR Part 56 (IRBs); US 21 CFR Part 54 (Financial Disclosure); International Conference for Harmonization (ICH) Guidance for Industry, E6(R2) GCP; the Nuremberg Code; and, where applicable the principles of the Declaration of Helsinki (Recommendations guiding Medical Doctors in Biomedical Research Involving Human Subjects), and with the NH&MRC National Statement on Ethical Conduct in Human Research (2007). The conduct of the study will be in accordance with the Notes for Guidance on Good Clinical Practice (CPMP/ICH/135/95), as adopted by the Australian Therapeutic Goods Administration (2000).

13.2 Ethics Committees

The investigator (or sponsor, where applicable) is responsible for ensuring that this protocol, the site's informed consent form, and any other information that will be presented to potential subjects (e.g., advertisements or information that supports or supplements the informed consent form) are reviewed and approved by the appropriate IRB or IEC. The investigator agrees to allow the IRB or IEC direct access to all relevant documents. The IRB or IEC must be constituted in accordance with all applicable regulatory requirements. The sponsor will provide the investigator with relevant documents or data needed for IRB or IEC review and approval of the study. Before investigational products and CRFs can be shipped to the site, the sponsor must receive copies of the IRB or IEC approval, the approved informed consent form, and any other information that the IRB or IEC has approved for presentation to potential subjects.

If the protocol, the informed consent form, or any other information that the IRB or IEC has approved for presentation to potential subjects is amended during the study, the investigator is responsible for ensuring that the IRB or IEC reviews and approves, where applicable, these amended documents. The investigator must follow all applicable regulatory requirements pertaining to the use of an amended informed consent form, including obtaining IRB or IEC approval of the amended form, before new subjects consent to take part in the study using the new version of the form. The investigator must promptly forward to the sponsor copies of the IRB or IEC approval of the amended informed consent form or other information and the approved amended informed consent form or other information and the consent forms must be obtained in addition to the approval given for the clinical study. Regulatory review and approval may be required in some countries before IRB or IEC approval can be sought.

13.3 General Considerations

The Investigator must conduct the study in accordance with this protocol and ICH GCP guidelines which have their origins in the Declaration of Helsinki. The Investigator and Tris Pharma will sign the protocol and study contract to confirm agreement. The Investigator will not implement any amendment (deviation or changes of the protocol) without agreement by Tris Pharma and the IRB approval/information, except where necessary to eliminate immediate

hazards to study subjects or when changes involve only logistical or administrative aspects of the study.

When any new and important information that may be relevant to the subject's consent is obtained, the Investigator and Tris Pharma will consult with each other on how to deal with the information. When Tris Pharma and a responsible Investigator judge it necessary, the Investigator must immediately provide the subjects with such information, revise the written information and other explanatory documents based on the new information, and obtain approval from the IRB(s). In this instance, the Investigator should also immediately inform subjects currently participating in the clinical study of such information, confirm their intention to continue participation, re-explain the study to them using the revised written information and other explanatory documents, and obtain written consent to continue participation based on their voluntary decision.

